7 DISCONTINUATION OF STUDY INTERVENTION AND PARTICIPANT DISCONTINUATION/WITHDRAWAL

7.1 Discontinuation of Study Intervention

An individual participant will not receive any further study intervention in the following situations.

- Participant decision. The participant is at any time free to discontinue study intervention, without prejudice to further treatment.

- An AE considered to jeopardize the safety of a participant in the study.
- Pregnancy.
- Severe noncompliance with the CSP.
- Development of any study specific criteria for discontinuation, including:
 - An anaphylactic reaction to the study intervention requiring administration of epinephrine.
 - A helminth parasitic infestation requiring hospitalization.
 - An asthma-related event requiring intubation.
 - Any malignancy except participants who develop basal cell carcinoma or localized squamous cell carcinoma of the skin, provided that the malignancy is excised and determined to have clean margins.
- Development of one or more of the following:
 - Confirmed ALT or AST increase of $\geq 8 \times$ ULN.
 - Confirmed ALT or AST increase of $\geq 5 \times$ ULN for more than 2 weeks.
 - Confirmed ALT or AST increase of $\geq 3 \times$ ULN and total bilirubin of $\geq 2 \times$ ULN.
 - ALT or AST of $\geq 3 \times$ ULN with the appearance of fatigue, nausea, vomiting, right upper quadrant pain or tenderness, fever, rash, and/or eosinophilia ($\geq 5\%$).

Note that discontinuation from study intervention is NOT the same thing as a withdrawal from the study.

Participants who discontinue study intervention should return to the study center and complete the procedures described for the IPD visit (refer to Section 1.3, SoA, IPD visit) at 4 weeks (± 3 days) post last study intervention administration. If the IPD visit occurs on the same date as the scheduled Visit 6 (Week 12), all IPD assessments should be performed, in addition to influenza antibodies and influenza vaccine administration. The participant should then return for the scheduled Visit 7 (Week 16) visit and have all scheduled assessments performed, including the influenza antibodies, as per the SoA.

All participants who discontinue study intervention should be encouraged to return for all regularly scheduled visits for safety and efficacy assessments.

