8.3.5 Adverse Events Based on Examinations and Tests

The results from the CSP mandated laboratory tests and vital signs will be summarized in the CSR.

Deterioration as compared to baseline in CSP mandated laboratory values, vital signs and

other safety assessments should therefore only be reported as AEs if they fulfill any of the SAE criteria, are the reason for discontinuation of treatment with the study intervention or are considered to be clinically relevant as judged by the investigator (which may include but not limited to consideration as to whether treatment or non-planned visits were required or other action was taken with the study intervention, eg, dose adjustment or drug interruption).

If deterioration in a laboratory value/vital sign is associated with clinical signs and symptoms, the sign or symptom will be reported as an AE and the associated laboratory result/vital sign will be considered as additional information. Wherever possible the reporting investigator uses the clinical, rather than the laboratory term (eg, anemia versus low hemoglobin value). In the absence of clinical signs or symptoms, clinically relevant deteriorations in non-mandated parameters should be reported as AE(s).

Any new or aggravated clinically relevant abnormal medical finding at a physical examination as compared with the baseline assessment will be reported as an AE unless unequivocally related to the disease under study.

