8.3.8 Disease Under Study

When collecting AEs, the recording of diagnoses is preferred, when possible, to recording a list of signs and symptoms. Asthma symptoms or signs, such as wheeze, cough, chest tightness, dyspnea, breathlessness and phlegm, will be recorded as AEs only when:

- The sign or symptom is serious according to definitions, see Appendix E 2.
- The participant discontinues the study due to the sign or symptom.
- The sign or symptom is new to the participant or not consistent with the participant's pre-existing asthma history (defined as within 1 year of Visit 1) as judged by the investigator.

CCI [REDACTED] should be recorded as an AE or SAE only if it fulfills any of the above criteria.

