4.6.2.2 Presentation

All AE summaries will be presented by actual treatment group for the safety analysis set. A by- participant listing of all AEs will be provided; AEs occurring during screening will be included in the listing, but not summarized separately. The number and percentage of participants with on-treatment and on-study AEs will be tabulated separately by system organ class and preferred term. An event that occurred one or more times during a period will contribute one observation to the numerator of the proportion. The denominator of the proportion will comprise all participants in the safety population. On-treatment AEs will also be summarized by intensity/severity and separately, by causality/relatedness (as determined by the investigator). Should a participant report the same preferred term/system organ class within multiple intensity/severity or causality/relatedness categories, the participant's worst occurrence (most severe/most related) will be tabulated. Serious AEs, AEs leading to death, AEs leading to discontinuation from study intervention, and commonly occurring AEs (defined as those occurring in >5% of subjects in either treatment group) will be summarized by treatment group. AESIs will also be summarized descriptively by treatment group; serious infections will be summarized as part of the SAE by SOC and PT table in the SOC of infections and infestations and not in a separate table.

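### A non-serious asthma worsening in keeping with the history, which makes a participant stop study intervention but not leave the study, meets no AE criterion in Protocol 8.3.8 and so is absent from the AE-based discontinuation table.

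*Protocol*

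**What the plan says.** Protocol 8.3.8 is a closed list. Asthma signs and symptoms become AEs only if at least one of three criteria is met. The first is seriousness, by the Appendix E 2 definitions. The second is the discontinuation criterion, which reads: "The participant discontinues the study due to the sign or symptom". The third covers symptoms that the investigator judges to be new for that person or out of keeping with their earlier asthma.

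Stopping study intervention is not on the list. Protocol 7.1 is explicit that it differs from leaving the study: "Note that discontinuation from study intervention is NOT the same thing as a withdrawal from the study". The same section adds: "All participants who discontinue study intervention should be encouraged to return for all regularly scheduled visits for safety and efficacy assessments".

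Protocol 8.3.2 keeps the distinction in the AE record, with one field for the action taken with study intervention and another for whether the AE caused withdrawal from the study.

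Protocol 9.4.3.1 and SAP 4.6.2.2 plan a summary by treatment group of "AEs leading to discontinuation from study intervention". Separately, the disposition summary in SAP 4.1.1.2 counts treatment discontinuations by arm and gives the reason.

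**The concern.** The criterion for recording the event and the table that reports it use different definitions of discontinuation. The table is built on stopping study intervention, while the recording rule for asthma symptoms is triggered only by leaving the study. The protocol asks participants who stop injections to remain, so the participant who complies best is the one whose event is not recorded. Someone who leaves the study over the same symptom does generate an AE. Recording then depends on retention rather than on what happened clinically.

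At stake is the completeness of one descriptive safety table, and of the general AE tables, for a reason for stopping that is closely tied to the disease under study. The primary antibody analyses are not involved.

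**Working it through.** The plan gives no figure for this point, so there is none to reproduce. The check is mainly a reading of the rules against each other.

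**Step 1. Run the possible cases through 8.3.8.**

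| Asthma worsening | Participant | Criterion met | AE recorded |
|---|---|---|---|
| Serious | any | first | yes |
| Non-serious, new or inconsistent with history | any | third | yes |
| Non-serious, consistent with history | leaves the study because of it | second | yes |
| Non-serious, consistent with history | stops study intervention because of it, stays in the study | none | no |

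Only the last row is a gap.

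**Step 2. Look for another route into the AE data.**

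- Protocol 8.3.5 counts deteriorations that "are the reason for discontinuation of treatment with the study intervention". This is the trigger missing from 8.3.8, but it applies to laboratory values, vital signs and other safety assessments, not to asthma symptoms.
- The physical examination rule in 8.3.5 does not help. A new or aggravated finding "will be reported as an AE unless unequivocally related to the disease under study".
- Appendix E 1 includes deterioration of a pre-existing condition in its general AE definition. Section 8.3.8 is the specific rule for asthma symptoms and restricts that definition.
- The third criterion gives limited cover here. Protocol 5.1.2 requires asthma that is not well controlled at entry, so much worsening may be consistent with the history.

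No visible route closes the gap.

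**Step 3. Scale.**

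Inputs: 50 participants per arm (Protocol 9.2). Protocol 2.2 gives rates from the 52-week Phase 3 study. All-cause discontinuation of the regimen was 6.8% on tezepelumab and 10.7% on placebo. AEs leading to permanent discontinuation occurred in 2.1% and 3.6%.

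- One omitted event: 1/50 = 2 percentage points of an arm.
- All-cause stopping, unscaled: 50 × 0.068 = 3.4 on tezepelumab and 50 × 0.107 = 5.35 on placebo.
- All-cause stopping, scaled to Week 16 on the assumption of a constant rate: 3.4 × 16/52 ≈ 1.0 and 5.35 × 16/52 ≈ 1.6.
- AE-related stopping: 50 × 0.021 = 1.05 and 50 × 0.036 = 1.8. Scaled in the same way, about 0.3 and 0.55.

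Neither pair measures the gap. The AE-related rates describe events that were recorded as AEs. The all-cause rates cover every reason for stopping, so on those borrowed rates the affected participants could only be some part of about 1.0 to 3.4 on tezepelumab and 1.6 to 5.4 on placebo, and possibly none. The documents do not say what share stopped for asthma.

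**The case against.** A reader might infer that all treatment stopped for worsening asthma disappears from both the AE tables and the discontinuation tables. The documents do not support that. Two of the three criteria operate whatever happens to treatment, and the disposition summary still counts the discontinuation with its reason.

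The remaining gap can be narrowed further. Seriousness in Appendix E 2 is broad. It includes important medical events that may jeopardize the participant, and the examples given include intensive emergency-room or home treatment of allergic bronchospasm. The asthma-specific stopping criterion in 7.1 is an event needing intubation, which would be expected to be serious. Another ground in 7.1 that could fit is an AE judged to jeopardize safety, which already calls the event an AE. What mainly remains is a participant's own decision to stop over familiar, non-serious symptoms.

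The difference from 8.3.5 is not in itself a contradiction, because protocols often handle disease symptoms separately. The contents list a section on assessing asthma exacerbations (8.1.3), and Protocol 2.1 says their number will be investigated. That text is redacted, so some of this worsening may be captured there by arm. Losing the causality rating also matters less than it seems, since Appendix E 3 classes deterioration of the disease from lack of effect as having no reasonable possibility of a causal link. The AE summaries are descriptive, and SAP 3.3.1 plans no p-values.

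All of this stands, and it limits the size of the point. It does not remove the mismatch between the second criterion of 8.3.8 and the planned table. The disposition summary is not a substitute, because it gives a reason without AE intensity, causality or onset.

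**Conclusion.** The point holds for one defined case: a non-serious worsening, consistent with the asthma history, that leads to stopping study intervention in a participant who stays in the study. Followed as written, 8.3.8 keeps that event out of the AE tables, including the table of AEs leading to discontinuation of study intervention. This rests on reading the criterion literally, which is justified because 7.1 and 8.3.2 both treat the two kinds of discontinuation as distinct.

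The number affected cannot be derived from the documents and is probably very small. Each omission moves an arm's rate by 2 percentage points if the arm has 50 participants.

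A reader might also infer a demonstrated bias between arms. That goes too far. Protocol 2.2 reports a 56% lower exacerbation rate on tezepelumab, which makes it plausible that omissions would fall more on placebo. But that figure concerns exacerbations, not non-serious symptoms that end treatment. If the inference were right, the table would under-count placebo and make tezepelumab look relatively worse, so it gives no ground for saying that a tezepelumab safety signal is hidden.

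**What to change.** In the second criterion of Protocol 8.3.8, insert 'study intervention or' before 'the study', so that either kind of discontinuation triggers an AE record. This brings the section into line with 7.1, 8.3.5 and 9.4.3.1 and with SAP 4.6.2.2. Then query sites about participants already recorded as stopping treatment for asthma, and have them enter the AE where one is missing.

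This changes only what is recorded. It touches no dose, stopping criterion, visit or procedure. The cost is a few more AE records, a short site query, and IRB/IEC approval of the wording under Appendix C 1, which can go with the next amendment.

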8.3.9 Reporting of Serious Adverse Events

All SAEs have to be reported, whether or not considered causally related to the investigational product, or to the study procedure(s). All SAEs will be recorded in the eCRF.

If any SAE occurs in the course of the study, investigators or other site personnel will inform the appropriate Parexel representatives within one day ie, immediately but **no later than 24 hours** of when he or she becomes aware of it.

The designated Parexel representative will work with the investigator to ensure that all the necessary information is provided to the AstraZeneca Patient Safety data entry site **within one calendar day** of initial receipt for fatal and life-threatening events **and within 5 calendar days** of initial receipt for all other SAEs.

For fatal or life-threatening AEs where important or relevant information is missing, active follow-up will be undertaken immediately. Investigators or other site personnel will inform Parexel representatives of any follow-up information on a previously reported SAE within one calendar day, ie, immediately but **no later than 24 hours** of when he or she becomes aware of it.

Once the investigators or other site personnel indicate an AE is serious in the EDC system, an automated email alert is sent to the designated Parexel representative.

If the EDC system is not available, then the investigator or other study site staff reports a SAE to the appropriate Parexel representative by telephone.

The Parexel representative will advise the investigator/study site staff how to proceed.

For further guidance on the definition of a SAE, see Appendix [E 2](#) of the CSP.

The reference document for definition of expectedness/listedness is the Investigator's Brochure for the AstraZeneca drug.

8.3.10 Pregnancy

All pregnancies and outcomes of pregnancy should be reported to AstraZeneca except for:

- If the pregnancy is discovered before the study participant has received any study intervention

8.3.10.1 Maternal Exposure

If a participant becomes pregnant during the course of the study, study intervention should be discontinued immediately.

Pregnancy itself is not regarded as an AE unless there is a suspicion that the investigational product under study may have interfered with the effectiveness of a contraceptive medication. Congenital anomalies/birth defects and spontaneous miscarriages should be reported and handled as SAEs. Elective abortions without complications should not be handled as AEs. The outcome of all pregnancies (spontaneous miscarriage, elective termination, ectopic pregnancy, normal birth or congenital anomaly/birth defect) should be followed up and documented even if the participant was discontinued from the study.

If any pregnancy occurs in the course of the study, then the investigator or other site personnel informs the appropriate Parexel representatives within **1 day**, ie, immediately but **no later than 24 hours** of when he or she becomes aware of it.

The designated Parexel representative works with the investigator to ensure that all relevant information is provided to the AstraZeneca Patient Safety data entry site **within 1 or 5 calendar days** for SAEs (see Section [8.3.9](#) and **within 30 days** for all other pregnancies).

The same timelines apply when outcome information is available.

The PREGREP module in the eCRF is used to report the pregnancy and the paper-based PREGOUT module is used to report the outcome of the pregnancy.

8.3.10.2 Paternal Exposure

Pregnancy of the participant's partners is not considered to be an AE. However, the outcome of all pregnancies (spontaneous miscarriage, elective termination, ectopic pregnancy, normal birth or congenital anomaly), occurring from the date of the first dose until 16 weeks (5 half-lives) after the last administration of study intervention, if possible, be followed up and documented in the Pregnancy Report Form. Consent from the partner must be obtained before

the Pregnancy Report Form is completed.

8.3.11 Medication Error

If a medication error occurs in the course of the study, then the investigator or other site personnel informs the appropriate Parexel representatives within **1 day**, ie, immediately but **no later than 24 hours** of when he or she becomes aware of it.

The designated Parexel representative works with the investigator to ensure that all relevant information is completed within **1** (Initial Fatal/Life-Threatening or follow-up Fatal/Life-Threatening) **or 5** (other serious initial and follow-up) **calendar days** if there is an SAE associated with the medication error (see Section [8.3.9](#)) and **within 30 days** for all other medication errors.

The definition of a Medication Error can be found in [Appendix E 4](#).

8.3.12 Medical Device Deficiencies

Device constituents of the combination product (APFS) are being provided for use in this study. In order to fulfil regulatory reporting obligations worldwide, the investigator is responsible for the detection and documentation of events meeting the definitions of medical device deficiency that occur during the study with the device constituent of the study drug combination product.

The definition of a deficiency in the device constituent of a combination product (APFS) is an inadequacy of a medical device with respect to its identity, quality, durability, reliability, safety, or performance. Medical device deficiencies include malfunctions, use errors, and issues with information supplied by the manufacturer. For simplicity, the term medical device deficiency will be used for deficiency in the device constituent of a combination product.

NOTE: Additional guidance, including expanded definitions, can be found in [Appendix F](#) of the protocol.

The AstraZeneca Report Form will be used to collect the deficiency as per the Parexel study-specific Investigator Manual.

8.3.12.1 Time Period for Detecting Medical Device Deficiencies

- Medical device incidents or malfunctions of the medical device will be detected, documented, and reported during all periods of the study in which the medical device is used.
- If the investigator learns of any medical device deficiency at any time after a participant has been discharged from the study, and such incident is considered reasonably related to a medical device provided for the study, the investigator will promptly notify the sponsor.

The method of documenting medical device deficiency is provided in [Appendix F](#) and the Parexel study-specific Investigator Manual.

8.3.12.2 Follow-up of Medical Device Deficiencies

- Follow-up applies to all participants, including those who discontinue study intervention.
- The investigator is responsible for ensuring that follow-up includes any supplemental investigations as indicated to elucidate the nature and/or causality of the deficiency.
- New or updated information will be recorded on the originally completed form with all changes signed and dated by the investigator.

8.3.12.3 Prompt Reporting of Medical Device Deficiencies to Sponsor

- Deficiencies associated with the device constituent part of the combination product should be reported to the Sponsor.
- Medical device deficiencies will be reported to the Sponsor within 24 hours after the investigator determines that the event meets the protocol definition of a medical device deficiency.
- The AstraZeneca Report Form will be sent to the sponsor via email
 - Medical device deficiency with an associated adverse event
 - [contact]
 - AstraZeneca complaint representative(s), as per the Parexel study-specific Investigator Manual

NOTE: For AEs and SAE's, the eCRF must also be populated - see Section [8.3.9](#).

- Medical Device Deficiency without an associated adverse or serious adverse event
 - AstraZeneca complaint representative(s), as per the Investigator Manual
- The Sponsor will be the contact for the receipt of medical device deficiency reports.

8.3.12.4 Regulatory Reporting Requirements for Device Deficiencies

- The investigator will promptly report all medical device deficiencies occurring with any medical device provided for use in the study in order for the sponsor to fulfil the legal responsibility to notify appropriate regulatory authorities and other entities about certain safety information relating to medical devices being used in clinical studies.
- The investigator, or responsible person according to local requirements (eg, the head of the medical institution), will comply with the applicable local regulatory requirements relating to the reporting of medical device deficiencies to the IRB/IEC.
- For further guidance on the definitions, see [Appendix F](#) of the CSP.

8.4 Overdose

For this study, any dose of study intervention greater than 700 mg SC within a 2-week period will be considered an overdose.

There is currently no specific treatment in the event of overdose of study intervention and possible symptoms of an overdose are not established.

- An overdose with associated AEs is recorded as the AE diagnosis/symptoms on the relevant AE modules in the eCRF and on the Overdose eCRF module.
- An overdose without associated symptoms is only reported on the Overdose eCRF module.

If an overdose on an AstraZeneca study intervention occurs in the course of the study, the investigator or other site personnel inform appropriate Parexel representatives immediately, but **no later than 24 hours** of when he or she becomes aware of it.

The designated Parexel representative works with the investigator to ensure that all relevant information is provided to the AstraZeneca Patient Safety data entry site **within one or 5 calendar days** for overdoses associated with an SAE (see Section 8.3.9) and **within 30 days** for all other overdoses.

